5.3 Case Ascertainment for BM Abnormality

Cases of BM fibrosis with associated clinical signs will be ascertained using electronic medical record review that will be blinded to romiplostim exposure status. Confirmation of the diagnosis of BM fibrosis will be verified by an evaluation of the results of BM biopsies and clinical presentation.

Reticulin and collagen fiber content information will be gathered from BM biopsies. Since BM biopsies are not routinely obtained when treating ITP patients, an estimate of the incidence rate of reticulin and collagen fiber content from this study would likely be inaccurate. For this reason the prevalence rate of reticulin and collagen fiber content and related grading among patients with BM biopsies stained for reticulin and collagen formation will be calculated. Only data from the first BM biopsy prior to romiplostim therapy will be included in the analysis to reduce bias. This analysis will be conducted by splenectomy status.

Adult chronic ITP patients in both the Exposed Cohort and Unexposed Cohort with both positive findings of reticulin and collagen fiber content and repeated BM biopsies will be

assessed to describe disease progression related to changes in reticulin and collagen fiber content in subsequent BM biopsies.

Incidence of BM abnormal findings (eg, PMF, reticulin, and collagen fiber content formation) will be assessed based upon only patients with BM data prior to and post romiplostim therapy.

The relationship between BM findings of reticulin and collagen fiber content and clinical/laboratory findings will be established using data 6 to 3 months prior to, 3 to 0 months prior to, 0 to 3 months post, and 3 to 6 months post-abnormal BM findings (please see [Section 12.9](#) regarding issues related to missing data).

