3.5 Number of Subjects

[figure not shown]
Based upon an exploratory feasibility analysis of the Danish database, the incidence of adult ITP in this country is 3/100,000 per year. Extrapolating this rate to all 3 Nordic countries, there will be 570 newly registered ITP patients per year. Record collection of ITP patients began in 1996; therefore, by the end of 2008, there will be an estimated 7410 patients with ITP. Assuming that 80% of adult ITP patients will have durable remission, 1482 will become chronic ITP patients. This number is reduced to 1408 due to an expected 5% patient attrition over time. By 2008, these patients will constitute the group of prevalent cases eligible for romiplostim. Assuming that the Exposed Cohort will include 25% of the 1408 subjects, 352 patients with chronic ITP will be exposed to romiplostim during the first year post-approval.

For the period 2008 to 2018, there will be 5700 incident cases of adult ITP. Following the assumptions mentioned above, 1140 will become chronic, 1083 will remain after the attrition, and a total of 271 adult chronic ITP patients will receive romiplostim.

In total, there will be 623 patients (4234 patient-years) in the Exposed Cohort. According to the study design, the Unexposed Cohort for adult chronic ITP patients will include 1860 patients, which will account for 12,700 patient-years of follow-up ([Figure 1](#)). This is a conservative estimation; the sample size could be larger if the market share of romiplostim is larger than 25% percent.

The number of subjects for the romiplostim-off-label exposure is unknown.

Figure 1. Estimation of Study Sample Size

*Remission includes subjects considered "cured", including acute cases, cases that underwent successful splenectomy, and cases successfully treated with non romiplostim compounds.

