6.2 Outcomes

There are many outcomes in the NCPRR. They are:

Primary Outcome Endpoints:

- Incidence of increased BM reticulin and/or BM fibrosis with associated clinical signs⁴, confirmed by findings in BM biopsies among adult chronic ITP patients
- Incidence of reticulin and collagen BM fibrosis (reticulin fibrosis and collagen fibrosis: SNOMED codes: M49000, M49001, M49020, M99611) with associated clinical signs, confirmed by findings in a BM biopsy among adults chronic ITP patients

Secondary Endpoints:

Clinical Endpoints:

- Average platelet counts prior to, during, immediately after treatment cessation, and following romiplostim therapy (study periods are defined in [Section 7.1](#))
- Incidence of thrombocytosis (laboratory confirmation of a platelet count $> 450 \times 10^9/L$) with/without adverse events among adult chronic ITP patients
- Incidence of thrombotic/thromboembolic events (ICD-10: 180, 126)
- Incidence of hematological malignancies (focused on AML and MDS)
- Incidence of clinically significant bleeding and/or receipt of rescue ITP medications for each predefined romiplostim treatment period ([Section 7.1](#))
- Incidence of concurrent leukocytosis and anemia (measured by laboratory test results taken within 4 weeks of each other)
- Description of platelet counts and dose adjustment in mcg/kg of romiplostim in patients with cITP according to dose adjustment rules specified in the European SPC

⁴ Clinical signs: any of the following: splenomegaly, hepatomegaly, leukocytosis, and cytopenia.

BM Endpoints:

- Prevalence of reticulin and collagen fiber content in the first BM biopsies of adult chronic ITP patients prior to romiplostim therapy by splenectomy status
- Incidence of collagen fibrosis with associated clinical signs confirmed by findings in BM biopsies among adult chronic ITP patients
- Incidence of PMF (primary myelofibrosis) (ICD-10: c94.5) according to the WHO diagnostic criteria in adult chronic ITP patients who have BM data prior to and/or post romiplostim therapy
- Overall and specific incidence of BM fibrosis, including reticulin and collagen fiber content formation, and PMF among adult chronic ITP patients with BM data prior to and/or post romiplostim therapy
- Association between the aforementioned primary and secondary clinical outcomes and BM abnormal findings

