7.3 Time at Risk

Time at risk for the NCPRR is defined as from time after initial romiplostim exposure to occurrence of outcomes listed in [Section 6.2](#). For patients without these study outcomes, the time at risk will be from the index date to death, loss to follow-up, or the end of study, whichever comes first.

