11. STUDY SIZE CONSIDERATION

A total estimate of 623 patients (4,234 patient-years) will comprise the Exposed Cohort. According to the study design, the Unexposed Cohort for adult chronic ITP patients will include 1860 patients, and will account for 12,700 patient-years of follow-up ([Figure 1](#)). This is a conservative estimation.

The study will compare chronic ITP patients who received romiplostim with those patients who do not receive romiplostim. This study will collect approximately 4,234 patient-years of romiplostim-exposed patient information during the 11 years of follow-up. Although the background incidence rate of study outcomes in chronic ITP patients is unknown, this sample size has a greater than 80% probability of detecting a difference in a range of relative risks from 2 to 4 where the background incidence ranges for 0.5% to 5%.

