12.6 Comparisons of Outcomes that are Dependent on BM Data

1) Frequency and incidence of increased BM reticulin and/or BM fibrosis with associated clinical signs⁵, confirmed by findings in a BM biopsy and 2) frequency and incidence of collagen fibrosis with associated clinical signs confirmed by findings in BM biopsies will be analyzed between the Exposed Cohort and Unexposed Cohort in all adults with chronic ITP:

⁵ Clinical signs: any of the following: splenomegaly, hepatomegaly, leukocytosis, and cytopenia.

- Since the sample size could be very small, the detailed description of each identified case will be listed in the report.
- If there is a sufficient sample size, a formal statistical analytic comparison, as described in [Section 12.4](#), will be conducted.

Description of prevalence rate of reticulin and collagen formation among chronic ITP patients:

- This analysis will be conducted based upon all eligible adult chronic ITP patients in the period prior to romiplostim treatment by splenectomy status. Only initial BM results will be used in the analysis to reduce potential selection bias caused by repeated testing for BM with abnormal findings.
- Prevalence of patients with reticulin and collagen formation in BM will be assessed. No comparison will be conducted; however, the descriptive analysis will be used to describe demographic characteristics, clinical features, and laboratory findings.

1) Frequency and incidence of chronic idiopathic myelofibrosis (primary myelofibrosis) according to the WHO diagnostic criteria, and 2) overall and specific incidence rates of BM fibrosis findings, including reticulin and collagen fiber content formation, and chronic idiopathic myelofibrosis in the Exposed Cohort and Unexposed Cohort in adult chronic ITP patients who have BM data prior to and post romiplostim therapy:

- Since the sample size could be very small for these outcomes, the detailed description of each identified case will be listed in the report.
- If there is a sufficient sample size (e.g., approximately 10 per treatment group for each covariate considered), a formal statistical analytic comparison, as described in [Section 12.4](#), will be conducted.

2) Association of splenomegaly and/or hepatomegaly with BM fibrosis and 2) association of changes in peripheral blood prior to and following the finding of reticulin and collagen fiber content or formation (reticulin grading 1 to 3):

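### The primary marrow-fibrosis rate counts unbiopsied time as event-free, so it is a minimum, and any cohort ratio would also carry any difference in case capture

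*Protocol*

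**What the plan says.** Section 6.2 lists as a primary endpoint "Incidence of increased BM reticulin and/or BM fibrosis with associated clinical signs", confirmed by biopsy findings. Section 1.1 makes its rate in romiplostim recipients the primary objective.

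Section 7.3 sets the denominator without any biopsy condition: "For patients without these study outcomes, the time at risk will be from the index date to death, loss to follow-up, or the end of" the registry. Section 12.6 says the endpoint "will be analyzed between the Exposed Cohort and Unexposed Cohort in all adults with chronic ITP", with a formal comparison only if numbers suffice.

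Section 5.3 states: "Since BM biopsies are not routinely obtained when treating ITP patients, an estimate of the incidence rate of reticulin and collagen fiber content from this" registry is likely to be inaccurate. For fiber content it turns to prevalence among biopsied patients, and for the incidence of abnormal marrow findings it uses only patients with marrow data before and after romiplostim. Section 5.5 bases the secondary marrow endpoints on patients with at least one stained biopsy. Neither restriction applies to the primary endpoint.

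Section 12.6 uses only initial marrow results "to reduce potential selection bias caused by repeated testing for BM with abnormal findings", but this safeguard belongs to the pre-romiplostim prevalence analysis. None of the four bias sources in Section 8 concerns who is biopsied.

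**The concern.** A patient who is never biopsied cannot enter the numerator but stays in the denominator until death, loss to follow-up or study end. That time is treated as known to be free of fibrosis when it was not assessed. The registry exists largely to quantify this risk, so a low rate could be read as reassurance when it partly reflects how seldom marrow was examined.

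The comparison has a second problem. If the share of true cases found by biopsy differs between cohorts, the rate ratio mixes drug effect with testing. Two statements make a difference plausible: Section 2.3 lists increased marrow reticulin among the key romiplostim risks, and Section 8 expects treated patients to have more severe and longer-standing disease. Adjusting for baseline severity by propensity score would not by itself remove a difference in biopsies taken after the index date.

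The clinical-sign condition may give little protection. Cytopenia alone qualifies and is not defined further. Section 3.4.2 requires a platelet count below 150 × 10⁹/L around diagnosis, so if thrombocytopenia counts as cytopenia, nearly every patient could meet the condition and biopsy would drive case finding.

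**Working it through.** **Inputs from the protocol.** Section 3.5: "In total, there will be 623 patients (4234 patient-years) in the Exposed Cohort"; the Unexposed Cohort "will include 1860 patients, which will account for 12,700 patient-years of follow-up". Section 11 claims that "this sample size has a greater than 80% probability of detecting a difference in a range of relative risks from 2 to 4" for background incidence of 0.5% to 5%. Appendix 1 gives the cells but no alpha. A two-sided 5% level is assumed here, in line with the 95% interval in the synopsis.

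**Step 1: reproduce the plan's power.** Treat event counts as Poisson. The total is N ~ Poisson(λ₀ × (RR × 4,234 + 12,700)). Given N, exposed events follow Binomial(N, RR × 4,234 / (RR × 4,234 + 12,700)). The null probability is 4,234/16,934 = 0.25. Reject when the upper-tail probability is at most 0.025, and average over N.

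- 0.5% background, RR 2: 89.6% (Appendix 1: 89).
- 1.0% background, RR 2: 99.6% (Appendix 1: 99).
- 29 of 30 cells agree within 2 points. The exception is 2.0%/RR 1.5 (99 stated, 94.2 computed), which lies outside the RR range in Section 11.

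These figures presume that every case in all 16,934 patient-years is found.

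**Step 2: effect of incomplete capture.** Let c be the share of true cases found through biopsy. Then:

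- observed rate = true rate × c;
- observed RR = true RR × c(exposed)/c(unexposed).

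At c = 20%, a true 10 per 1,000 patient-years shows as 2 per 1,000.

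**Step 3: cohort comparison.** The capture shares are assumptions, because the protocol gives none. The true rate is 1% per year and the true RR is 1. Expected events are 0.01 × c × patient-years.

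| Capture, exposed v unexposed | Expected events | Observed RR | Chance of false upper signal |
|---|---|---|---|
| 20% v 20% | 8.5 v 25.4 | 1.0 | 1.6% |
| 30% v 20% | 12.7 v 25.4 | 1.5 | 17% |
| 40% v 20% | 16.9 v 25.4 | 2.0 | 51% |
| 10% v 20% | 4.2 v 25.4 | 0.5 | about 0% |

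In the last row's setting, a true RR of 2 would appear as 2 × 10/20 = 1.0.

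**Step 4: absolute exposed rate.** With zero events, the approximate upper 95% bound is 3/patient-years. Here f is the assumed share of exposed time assessed, with biopsy taken to be unrelated to disease.

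- f = 100%: 3/4,234 = 0.07 per 100 patient-years.
- f = 50%: 3/2,117 = 0.14.
- f = 20%: 3/847 = 0.35.
- f = 10%: 3/423 = 0.71.

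**Step 5: price of using only biopsied person-time.** With 20% biopsied in each cohort (847 v 2,540 patient-years), power for RR 2 falls from 90% to 26% at 0.5%, and from 99.6% to 51% at 1%. At 2% it is 82%.

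**The case against.** The strongest reply is that a registry may properly report clinically manifest, biopsy-confirmed cases per patient-year of treated patients. On this view, the Section 5.3 sentence is about fiber content without a clinical-sign condition, not about the primary endpoint. That reading of the sentence is correct, so a reader should not infer that the protocol calls its own primary endpoint inaccurate. What carries over is the stated fact that biopsy is not routine.

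A reader might also infer that the protocol says the cohorts are biopsied unequally. It does not. Sections 2.3 and 8 make this plausible but give no frequency.

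Biopsied-patient incidence analyses are already planned for secondary outcomes, and Sections 12.4 and 12.8 treat comparisons as exploratory and call for caution. These points stand and lower the stakes of the ratio. They leave the primary denominator unchanged. Section 3.1 still provides for an urgent report if an annual assessment shows a significant risk.

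Blinded review, independent re-reading and requested staining standardise the biopsies that exist; they do not address who was biopsied. Section 12.9 relies on charts to fill in missing outcomes, but a chart cannot supply a biopsy that was never done.

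Finally, restricting the comparison to biopsied patients is no clean cure. It conditions on an event after exposure. If exposed patients were biopsied for monitoring and unexposed patients on suspicion, a true signal could be diluted.

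**Conclusion.** The point holds in this form: as written, the primary exposed rate is a minimum rate of detected cases, and the protocol neither says so nor describes its denominator by biopsy status. This needs no assumption about differences between cohorts, only that some true cases go unbiopsied.

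The effect on the ratio is conditional. It equals the capture ratio, and its size and direction cannot be fixed from the document. The 17% and 51% figures rest on a true rate of 1% per year, 20% unexposed capture and a two-sided 5% test that the protocol does not prescribe. The 0.35 bound rests on 20% assessed time and biopsy unrelated to disease; if biopsy is aimed at suspected cases, capture is higher and the gap is smaller.

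It is tempting to read the 1.0% row of Appendix 1 as false-signal chances of 70% and 99% for capture ratios of 1.5 and 2. That would treat 1.0% as the detected unexposed rate. With 20% capture, a true 1.0% is detected as 0.2%, where Appendix 1 gives 16% and 50%, close to the 17% and 51% above.

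**What to change.** In Section 12.6, for the primary endpoint:

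- Report biopsies per patient-year and the proportion of patients biopsied after the index date, by cohort and follow-up period, from the pathology registry data named in Section 5.5.
- Beside the all-patient rate, show the result among patients with at least one stained biopsy after the index date, as a sensitivity analysis, with the reason for biopsy where the chart gives it.
- Label the all-patient rate as a minimum rate of clinically detected cases.
- State that the two analyses are read together and that neither ratio alone is taken as a drug effect.

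In Section 8, add biopsy selection as a source of bias.

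The cost is some wording and a few tables from data the registry already plans to use; no additional biopsies are implied. The downside is that the biopsied-patient analysis is itself selected and has much lower power, so it qualifies the all-patient result and should not replace it.

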5.4 Ascertainment for Laboratory Data Outcomes

The effect of romiplostim on thrombocytosis and worsened thrombocytopenia after cessation of romiplostim therapy will be assessed based upon laboratory data. The NHRS contains all laboratory testing results. The study will review all electronic laboratory results through 4 predefined romiplostim study time periods. Two types of data will be obtained: 1) average level of platelet counts for each predefined time period; and 2) frequency of platelet counts above or below the normal range for each predefined time period. Thrombocytosis will also be confirmed by electronic medical chart review, and will be assessed whether it occurs with an adverse experience or not. In addition, rescue medication data for thrombocytopenia will also be obtained, and will be used to adjust for treatment effects in different study periods.

5.5 Standard Review of BM Biopsies and Related Study Plan for Patients with BM Biopsy

BM biopsy-related secondary endpoints of the NCPRR will be based upon all ITP patients who have at least 1 BM biopsy stained for reticulin and collagen registered in the National Pathology Registry (SNOMED: T06000, T06001, T06002 and/or S45410). For the purpose of NCPRR BM study requirements, all BM specimens for adult chronic ITP patients will be requested to be stained for reticulin and collagen.

To ensure these standards, 2 pathologists will independently re-review all BM biopsy specimens. If diagnostic conclusions for a BM biopsy from both pathologists are inconsistent, a third pathologist will re-review the specimen to achieve a final diagnosis. All reviews will be blinded to romiplostim treatment status.

6. DEFINITION OF EXPOSURE, OUTCOME, AND OTHER STUDY VARIABLES

6.1 Exposure

Exposure is defined as the patient receiving romiplostim therapy.

6.2 Outcomes

There are many outcomes in the NCPRR. They are:

Primary Outcome Endpoints:

- Incidence of increased BM reticulin and/or BM fibrosis with associated clinical signs⁴, confirmed by findings in BM biopsies among adult chronic ITP patients
- Incidence of reticulin and collagen BM fibrosis (reticulin fibrosis and collagen fibrosis: SNOMED codes: M49000, M49001, M49020, M99611) with associated clinical signs, confirmed by findings in a BM biopsy among adults chronic ITP patients

Secondary Endpoints:

Clinical Endpoints:

- Average platelet counts prior to, during, immediately after treatment cessation, and following romiplostim therapy (study periods are defined in [Section 7.1](#))
- Incidence of thrombocytosis (laboratory confirmation of a platelet count $> 450 \times 10^9/L$) with/without adverse events among adult chronic ITP patients
- Incidence of thrombotic/thromboembolic events (ICD-10: 180, 126)
- Incidence of hematological malignancies (focused on AML and MDS)
- Incidence of clinically significant bleeding and/or receipt of rescue ITP medications for each predefined romiplostim treatment period ([Section 7.1](#))
- Incidence of concurrent leukocytosis and anemia (measured by laboratory test results taken within 4 weeks of each other)
- Description of platelet counts and dose adjustment in mcg/kg of romiplostim in patients with cITP according to dose adjustment rules specified in the European SPC

⁴ Clinical signs: any of the following: splenomegaly, hepatomegaly, leukocytosis, and cytopenia.

BM Endpoints:

- Prevalence of reticulin and collagen fiber content in the first BM biopsies of adult chronic ITP patients prior to romiplostim therapy by splenectomy status
- Incidence of collagen fibrosis with associated clinical signs confirmed by findings in BM biopsies among adult chronic ITP patients
- Incidence of PMF (primary myelofibrosis) (ICD-10: c94.5) according to the WHO diagnostic criteria in adult chronic ITP patients who have BM data prior to and/or post romiplostim therapy
- Overall and specific incidence of BM fibrosis, including reticulin and collagen fiber content formation, and PMF among adult chronic ITP patients with BM data prior to and/or post romiplostim therapy
- Association between the aforementioned primary and secondary clinical outcomes and BM abnormal findings
- Association of changes in peripheral blood with listed BM abnormal findings (3 to 6 months prior to, 0 to 3 months prior to, 0 to 3 months post, and 3 to 6 months post-abnormal BM findings)

Romiplostim Off-label Use

- Romiplostim utilization in patients without adult chronic ITP assessed by underlying disease for which the drug is used.

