1.2 Secondary Objectives

Potential clinical risks:

- To describe the phenomenon of worsened thrombocytopenia (platelet count significantly reduced to, or below, baseline platelet count levels) after romiplostim cessation among adult chronic ITP patients
- To study the incidence rate of thrombocytosis (platelet count $> 450 \times 10^9/L$) among romiplostim-treated adult chronic ITP patients with/without adverse events
- To describe the incidence rate of thrombotic/thromboembolic events and the distribution of specific diagnoses of these thrombotic/thromboembolic events for a romiplostim-exposed cohort and an unexposed cohort
- To assess the incidence rate of hematological malignancies and pre-malignant states (focused on acute myelogenous leukemia [AML] and myelodysplastic syndromes [MDS]) for a romiplostim-exposed cohort and an unexposed cohort
- To describe clinically significant bleeding and/or receipt of rescue medication (any new ITP medication prescribed to a chronic ITP patient during romiplostim therapy) in predefined romiplostim therapy periods ([Section 7.1](#))
- To describe the incidence rate of concurrent leukocytosis and anemia (measured by laboratory test results taken within 4 weeks of each other)

³ Clinical signs: any of the following: splenomegaly, hepatomegaly, leukocytosis, and cytopenia

- To describe patient safety profiles, including the incidence rate of renal failure among adult chronic ITP patients with renal impairment medical condition when romiplostim therapy is initiated
- To measure the impact of the EU dosing rule in the cohort of romiplostim exposed patients

Potential BM abnormal findings:

- To describe the prevalence of reticulin and collagen fiber content in the first BM biopsy of adult chronic ITP patients prior to romiplostim exposure, by splenectomy status
- To assess the incidence of collagen fibrosis with associated clinical signs confirmed by findings in BM biopsies of adults with chronic ITP either receiving or not receiving romiplostim
- To study the incidence of chronic idiopathic myelofibrosis (CIMF, primary myelofibrosis) according to the WHO diagnostic criteria in adults with chronic ITP either receiving or not receiving romiplostim

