- A hypothetical concern regarding hematopoietic growth factors is that they may enhance the growth of existing malignancies or promote the growth of new malignancies that are influenced by the receptor-ligand axis. The TPO receptor is predominantly expressed on cells of the myeloid lineage, and there is no confirmed expression on solid tumors ([Graf et al, 1996](#); [Columbyova et al 1995](#)); therefore, it is not expected that romiplostim will promote the growth of solid tumors. In the ITP clinical program, there is no evidence of increased neoplasia, including hematopoietic malignancies; there is, however, a potential risk that TPO receptor agonists may stimulate the progression of existing hematopoietic malignancies or MDS among patients with thrombocytopenia caused by conditions other than ITP. Ongoing clinical studies in other patient populations, including MDS, will help to assess this potential risk.

Other potential risks include:

- Thrombotic/thromboembolic complications
- Progression of increased reticulin to an irreversible BM fibrotic state

In Europe, the product label includes further dose adjustment rules that have been specified by the European regulator as a risk minimization measure of thromboembolic risk and have not been tested in clinical trials.

Dose adjustment rules as specified in the European label

Platelet count (x 10 ⁹ /L)	Action
<50	Increase once weekly dose by 1 mcg/kg
>150 for 2 consecutive weeks ^a	Decrease once weekly dose by 1 mcg/kg
>250 ^a	Do not administer, continue to assess platelet count weekly After the platelet count has fallen to < 150 x 10 ⁹ /L, resume dosing with once weekly dose reduced by 1 µg/kg

^a Due to the inter-individual variable platelet response, in some patients platelet count may abruptly fall below 50 x 10⁹/L after dose reduction or treatment discontinuation. In these cases, if clinically appropriate, higher cut-off levels of platelet count for dose reduction (200 x 10⁹/L) and treatment interruption (400 x 10⁹/L) may be considered according to medical judgment

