3. PATIENT REGISTRY STUDY PLAN

3.1 Registry Design

The NCPRR is established on the basis of the NHRS of 3 Nordic countries: Denmark, Sweden, and Norway.

The study period will be between 01 January 2009 (starting date) and 31 December 2019 (ending date). Interim study reports will be developed for yearly submission to the Agency. Each annual report will describe include events occurring from 01 January through 31 December of the reporting period with cumulative results. All data sources will use the same cutoff date in calendar time, December 31st of the latest year for all data obtained from the NHRS databases. The patient experience (patient time) for all patients who receive at least 1 dose of romiplostim therapy will be included in the romiplostim exposure cohort after they receive romiplostim. The patient experience with ITP time before romiplostim exposure will be included in the romiplostim unexposed cohort, along with that for all adult chronic ITP patients who never receive romiplostim therapy during the study period.

Adult chronic ITP cohorts (romiplostim Exposed Cohort and Unexposed Cohort) include adult patients who are identified as having chronic ITP (incident and prevalent cases through both hospital discharge registry and outpatient clinic registry, as described by [Frederiksen and Schmidt, 1999](#)) on or after the starting date, and up to 1 year prior to the ending date. All patients will be followed-up for **at least 1 year and up to 11 years** in either of 2 cohorts: the romiplostim Exposed Cohort or Unexposed Cohort. Incident and recurrent outcomes of interest will be assessed on an annual basis.

All clinical outcomes (eg, thrombotic/thromboembolic events, hematological malignancies, and other potential outcomes of interest) will be identified by International Classification of Diseases – 10th Revision (ICD-10) codes from the NHRS databases (eg, hospital discharge registry, outpatient clinic registry, pathology registry, death registry, cancer registry, birth registry, and prescription registry) or by review of electronic medical records and/or paper medical charts. As needed, suspected and identified cases will be medically confirmed by review of electronic medical records and/or paper medical charts, laboratory testing results, BM biopsy reports, pathology data, pharmacy data, and other relevant health records. Laboratory data will be used to determine thrombocytosis and worsened thrombocytopenia after cessation of romiplostim.

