5.2 Case Ascertainment for Clinical Events

Clinical events (eg, bleeding, thromboembolic, and hematological malignancy endpoints) will be identified and ascertained by ICD-10 diagnostic codes and/or relevant laboratory and pathology data. The detailed diagnostic codes will be provided by the study statistical analysis plan (SAP). All identified cases will be confirmed using electronic medical record review that will be blinded to romiplostim exposure. Patients observed with one of the outcomes of interest during the study will be continually followed for other outcomes until the end of study, death, or loss to follow-up, whichever comes first.

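### The thromboembolic endpoint names only two ICD-10 categories, which is narrower than its objective and at odds with leaving the detailed codes to the SAP

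*Protocol*

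**What the plan says.** **Objective.** Section 1.2 of the protocol, and the synopsis in almost the same words, sets the aim "To describe the incidence rate of thrombotic/thromboembolic events and the distribution of specific diagnoses of these thrombotic/thromboembolic events for a romiplostim-exposed cohort" and for an unexposed cohort. No event type is left out.

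**Endpoint.** Section 6.2 and the synopsis list of secondary endpoints both read "Incidence of thrombotic/thromboembolic events (ICD-10: 180, 126", after which the parenthesis closes. Neither place has *eg*, *including* or a reference to a fuller list.

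**Ascertainment.** Section 5.2 states that clinical events, with thromboembolic endpoints named among them, "will be identified and ascertained by ICD-10 diagnostic codes and/or relevant laboratory and pathology data". It adds: "The detailed diagnostic codes will be provided by the study statistical analysis plan (SAP". Section 3.1 lets clinical outcomes be identified from registry codes "or by review of electronic medical records and/or paper medical charts". Section 5.2 then requires: "All identified cases will be confirmed using electronic medical record review that will be blinded to romiplostim exposure".

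**Standing of the risk.** Section 2.3 lists "Thrombotic/thromboembolic complications" among the potential risks, and describes the European dose adjustment rules as a measure against thromboembolic risk. Measuring the impact of those rules is a separate secondary objective.

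**The concern.** An endpoint should deliver its objective. Here the objective is broad and asks for a breakdown by diagnosis, while the endpoint is tied to two categories. If the analysis follows the endpoint text, two things go wrong. Events coded elsewhere drop out of the numerator, so the rate of a named potential risk is understated. The distribution of specific diagnoses also becomes a distribution within two categories, which is not what Section 1.2 promises.

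The external comparison suffers too. Section 12.8 sets the exposed-cohort rates against other sources, including a Danish study of bone marrow fibrosis and thrombotic/thromboembolic event rates. If the event definition is narrower on one side than on the other, part of any difference comes from the definition.

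**Working it through.** **Step 1. Does the parenthesis define the endpoint or give examples?**

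- Elsewhere in Section 6.2, codes in parentheses identify the endpoint: four SNOMED codes for reticulin and collagen fibrosis, and one ICD-10 code for primary myelofibrosis.
- Where the protocol means an open list it usually says so with *eg*, as in Sections 3.1, 5.2 and 6.3. The malignancy endpoint in Section 6.2 uses *focused on*.
- The thromboembolic bullet has neither, so its natural reading is a definition.

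**Step 2. Can the three places be reconciled as written?**

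| Place | Scope |
|---|---|
| Section 1.2 and synopsis objective | All thrombotic/thromboembolic events, plus their specific diagnoses |
| Section 6.2 and synopsis endpoint | Two ICD-10 categories |
| Section 5.2 | Detailed codes to come from the SAP |

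If the SAP lists only codes within the two categories, it meets Section 6.2 but not Section 1.2. If it lists more, it meets Section 1.2 but departs from Section 6.2. Either way one protocol statement fails.

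**Step 3. Do the other routes to identification remove the limit?** Chart, laboratory and pathology review can bring further events to light, but the endpoint definition decides whether they count. The blinded confirmation in Section 5.2 applies to cases already identified, so it removes false positives and does not by itself add uncoded events.

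**Step 4. How large could the effect be?** Let f be the share of events that fall in the two categories. The observed rate is f times the true rate. If f is the same in both cohorts, the rate ratio is unchanged but rests on fewer events. The documents do not give f, so this step is an illustration only.

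Inputs from Section 11 and Appendix 1: 4,234 exposed and 12,700 unexposed patient-years; background rate b = 0.5% per year; relative risk RR = 2; stated power 89%. Assumed, because Appendix 1 does not state it: two-sided alpha of 0.05.

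Method: exact conditional test of two Poisson rates. Given N events in total, the exposed count is binomial with probability

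- under no effect: 4,234 / (4,234 + 12,700) = 0.250
- under RR = 2: 2 × 4,234 / (2 × 4,234 + 12,700) = 8,468 / 21,168 = 0.400

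N is Poisson with mean f × b × (12,700 + RR × 4,234) = f × 0.005 × 21,168 = f × 105.84. Power is averaged over N.

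The plan's own figure first: at f = 1 the result is 89.6%, against 89% stated, so that figure reproduces.

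| f (assumed) | Expected exposed events, 4,234 × 0.005 × 2 × f | Power, b = 0.5%, RR 2 | Power, b = 1%, RR 2 |
|---|---|---|---|
| 1 | 42.3 | 89.6% | 99.6% |
| 0.75 | 31.8 | 79.0% | 97.7% |
| 0.50 | 21.2 | 61.0% | 89.6% |
| 0.25 | 10.6 | 32.9% | 61.0% |

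At a background of 0.5%, missing about a quarter of events takes the power just below the 80% claimed in Section 11. At 1%, it stays above 80% even if half are missed.

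**The case against.** The strongest reply is that Section 5.2 makes the SAP the home of the code list. The SAP is not at hand, and it may well list every relevant code. Charts are abstracted for chronic ITP patients seen in hospital in each reporting period (Section 5.1), and chart review is an accepted way to identify outcomes. The study is declared descriptive, and this is one secondary endpoint among many. On this view the parenthesis is loose wording.

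Much of that stands, and it rules out several stronger readings that a reader might infer:

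- *The endpoint is fixed to two codes and most event types would be lost.* Not established. Section 5.2 leaves room for a fuller list, and the documents give no mix of event types from which *most* could follow.
- *The codes select nothing because they lack a letter.* Codes elsewhere in the protocol are in letter-digit form, so the missing letter is probably an effect of reading the PDF. It is not counted as an error here.
- *Only venous events are covered, so an increase in arterial events would be invisible.* This needs an assumed correction of the codes to I80 and I26, and a classification that the protocol does not reproduce. The chart, laboratory and pathology routes also tell against it. The mismatch in scope does not depend on it.

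The reply does not remove the restriction in the protocol's own endpoint text. Nor does Section 10 fill the gap: its chart reviewers report adverse events documented as linked to romiplostim, which is safety reporting and cannot supply an incidence rate for the unexposed cohort.

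**Conclusion.** The point holds as an inconsistency with a possible consequence. The endpoint text in Section 6.2 and the synopsis is narrower than the objective and conflicts with the deferral of codes in Section 5.2. If it is followed as written, events outside the two categories are not counted and the breakdown by diagnosis cannot be given.

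No undercount has been demonstrated, and its size cannot be derived from the documents. The power figures rest on assumed capture shares, an assumed alpha and equal capture in both cohorts. They show how the result would respond to a loss of events and do not estimate that loss. Section 11 itself says the background incidence is unknown.

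The change should be made: the risk is one the registry was set up to follow, and the correction is small.

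**What to change.** In Section 6.2 and in the synopsis, replace the two-code parenthesis with *all arterial and venous thrombotic/thromboembolic events, per the SAP code list*. State that the total and the specific diagnoses will be reported for both cohorts, as the objective requires. Section 5.2 can then stand as it is.

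The cost is a wording change in two places, a longer code list and some additional charts to confirm.
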